1.2 Secondary & Tertiary Objectives

Compared to a visual imagery intervention group, the participants who are enrolled in the motor imagery intervention group will show:

- Significant improvements in cognitive performance during Talking and Walking While Talking
- Changes in blood-oxygen-level dependent signal during Walking and Walking While Talking
- Improvement in executive function, and other mobility-related cognitive processes, such as speed of processing, memory and spatial navigation.
- Improved gait variability and other quantitative gait parameters during walking and walking while talking.

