2.1 Study Rationale

Motor imagery involves envisioning motor actions without actual execution, and has been successfully used by athletes to improve athletic performance for quite some time; for reviews see

(9-12). There is some evidence that *motor imagery* can be used to improve gait, gait-related and cognitive functions in Parkinson's disease (13-15) and post stroke (16-20), but the rehabilitative potential of motor imagery in relatively healthy elderly is currently unknown.

Recent research suggests that gait engages a distributed network of brain regions including motor, basal ganglia, cerebellar and supplementary motor regions. Based on recent findings by us (21) and others (22, 23), we hypothesize that imagined gait can be used as a rehabilitative tool for improving gait in the elderly because it engages and strengthens similar neural systems as actual gait. Age-related gait decline is particularly evident in dual-task situations that demand Executive Functions (EF) and engage the prefrontal cortex (24-31). We recently developed and validated an imagined gait protocol against an actual gait protocol that involves an ecologically-valid dual-task situation (walking while talking; WWT) that predicts falls, frailty, disability and mortality in the elderly (21, 31, 32). This imagined gait protocol involves: 1) imagined Walking (iW), imagined Talking (iT) and imagined Walking While Talking (iWWT), 2) is associated with actual WWT performance, and 3) permits us to examine the underlying neural systems of gait with functional magnetic resonance imaging (fMRI). We have identified a pattern of brain regions whose activation change as a function of imagery task difficulty (iW < iT < iWWT), and is associated with actual WWT performance (21). Increases were most notably observed in cerebellar, precuneus, supplementary motor and prefrontal cortex regions. These initial findings suggest that our imagined gait protocol engages similar neural systems as actual gait and EF and command the development of this protocol into a tool for improving gait and EF in the elderly.

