The first aim of this research is to establish the efficacy of this imagined gait protocol to improve gait and EF in the elderly. We propose a pilot Randomized Clinical Trial (RCT) of 48 cognitively-healthy elderly adults who will be randomly assigned to an imagined gait intervention or an Active Control (AC; non-mobility related visual imagery) condition. The imagined gait (or AC) protocol will be administered during each study visit, and over the phone three times a week for three months (15 min/session, total of 36 sessions). Each participant will complete two study visits (pre and post). Pre-post intervention changes in gait velocity (cm/s) and cognitive performance (percent of correct letters provided; (correct/error x correct) x 100) during actual W, T and WWT will be our primary outcome measures. Age, Sex and Education will be covariates in all analyses. Other variables/covariates will be recorded (e.g. medical illnesses and history of falls), and carefully examined for potential inclusion as covariates in upcoming full-scale RCT.

The second aim is to determine neuroplasticity changes in response to our imagined gait intervention. To this end, participants will complete the imagined gait protocol (iW, iT and iWWT) during fMRI scanning at the pre and post-intervention study visits. We predict that our imagined gait protocol engages neural systems linked to actual gait and EF, while the AC condition engages neural systems linked to visual processing and imagery in general. We further predict that the neural systems engaged during our imagined gait protocol are strengthened following our imagined gait intervention.

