Cognitive performance during the WWT – number of correct letters generated during WWT will be the main cognitive outcome. Additional cognitive/executive function tasks, including the WAIS-III Letter Number Sequencing Test (46), Stroop Color and Word Test (47), Trail Making Test (48) and Flanker Interference Task (49) will also be administered to determine if there are any far-transfer effects of our imagined gait intervention, and to carefully identify appropriate outcome measures for upcoming studies. Improved performance on the Stroop test following motor imagery training has been shown in individuals with Parkinson's disease (13), and we have previously shown improved performance on the Letter Number Sequencing Task in cognitively-healthy older adults following a cognitive intervention (50). Additional neuropsychological measures of processing speed, language, and memory will also be examined (see ee Clinicaltrials.gov-NCT02762604 for a comprehensive list).

Change in blood-oxygen-level-dependent (BOLD) signal will be examined during single (imagined walking) and dual task (imagined walking-while-talking) walking conditions. Changes in BOLD signal has been shown following physical and cognitive interventions in the past (51-53).

Additional variables/potential covariates will be recorded and carefully examined for potential inclusion as covariates or outcome measures in upcoming full-scale RCT, including stride length (cm), double support time (s), cadence (steps/min), swing time (s), stance time, stride length variability (SD), swing time variability (SD), the Geriatric Depression Scale (54), Medical Illnesses and Medication questionnaires (26, 55), Cognitive and Physical leisure activity questionnaire (56-58), Falls (59), Obesity (assessed with weight, waist circumference, and BMI (kg/m^2)), Vision (Snellen's chart), Disability (7 ADLs using the scale developed by Gill and colleagues (60, 61), IADL (62, 63), Blood pressure (Sitting/Standing), Gray Matter Volume/Atrophy (T1-Weighted structural images) White Matter Integrity (Diffusion Tensor Imaging; DTI) and White Matter Hyper intensities (Fluid-Attenuated Inversion Recovery; FLAIR).

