function systems change as a function of our imagined gait versus the active control condition. This is also because changes in neural activation are often masked by between-subject variability, an issue that is particularly important to consider in aging populations (68, 69). Our multivariate analyses will be performed with software developed by my co-mentor in advanced neuroimaging analysis, [name]: http://www.nitrc.org/projects/gcva_pca. OrT-CVA will be used to identify covariance patterns in the fMRI signal as a function of trial type (iT, iW and iWWT) at each study visit (pre and post-intervention) for each imagery condition (imagined gait or AC). OrT-CVA is similar to other covariance analyses such as partial least squares (70, 71) in that it employs a principal components analysis (PCA) to the data matrix that is then transformed to a matrix of the experimental design. Linear regression is then applied to detect a covariance pattern, or ordinal trend, in the fMRI signal as a function of task conditions that is based on a linear combination of a small set of principal components. An ordinal trend is a monotonic change in pattern expression as a function of task conditions, in this case as a function of trial type (iW, iT and iWWT). The expression of an ordinal trend is quantified in terms of a participant-specific expression score that is derived by projecting the covariance pattern onto a participant's scan for each task condition. These participant-specific (or pattern) expression scores can also be used for further analysis (e.g. to correlate with actual WWT performance). Note that the proposed multivariate analyses of fMRI data involve data reduction and therefore does not involve multiple comparisons.

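### The planned ordinal-trend analysis of BOLD is insensitive to a similar training gain in imagined walking and imagined walking while talking, and Section 9.4 names no between-arm test of change in those two conditions

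*Combined protocol and SAP*

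**What the plan says.** **Outcome.** Section 1.2 lists as an objective, motor imagery against visual imagery, "Changes in blood-oxygen-level dependent signal during Walking and Walking While Talking". Section 9.1.2 defines it on the imagery tasks: the BOLD "signal will be examined during single (imagined walking) and dual task (imagined walking-while-talking) walking conditions". Section 2.1 (Study Rationale) gives the expected direction for Aim 2: "We further predict that the neural systems engaged during our imagined gait protocol are strengthened following our imagined gait intervention".

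**Analysis.** Section 9.4.2 names one BOLD analysis, OrT-CVA. It looks for covariance patterns over trial type, at each visit and for each arm. "An ordinal trend is a monotonic change in pattern expression as a function of task conditions, in this case as a function of trial type". Section 2.1 gives the order, by difficulty, from the group's earlier work: "We have identified a pattern of brain regions whose activation change as a function of imagery task difficulty (iW < iT < iWWT"). Section 9.4.2 gives no numeric weights for the trend. It says the method produces a score per participant for each task condition and that these scores may be analysed further. Its one example is correlation with actual walking-while-talking performance.

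**Sample size.** Section 9.2 bases the BOLD numbers on something else: an SPM second-level difference in contrast values between groups, described as a main effect of imagery condition, needing 16 per group. Section 9.4 does not mention that comparison again.

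**The concern.** The outcome concerns signal level in two walking tasks, and how it changes from pre to post between arms. The named parameter is a gradient across three tasks, with a task that involves no walking in the middle and the two walking tasks at opposite ends. A training effect that lifts both ends by a similar amount leaves the end-to-end gradient where it was.

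If the intervention strengthens the walking-imagery response in both tasks, the trend may look unchanged or less orderly, and the report could conclude that there was no gait-related BOLD change. A change that does appear in the trend could come from the talking or executive load that separates iWWT from iW. No stated arm-by-visit comparison of iW and iWWT stands beside the trend to settle the matter.

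**Working it through.** **1. The plan's own BOLD figure.** Section 9.2 states 16 per group at p < 0.001 and power 0.80, with one group's mean signal change half the other's. It gives a first-level signal change of 0.34% but no between-subject SD, so the figure cannot be reproduced. Taking the difference as 0.34%/2 = 0.17% (my reading), n per group = 2(3.29 + 0.84)² × SD²/0.17² (two-sided, normal approximation). This gives 16 when SD is about 0.116%. SDs of 0.10%, 0.15% and 0.20% give 12, 27 and 48. The calculation concerns a between-group contrast and says nothing about the power of a trend over tasks.

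**2. Algebra of the trend.** Order the scores (iW, iT, iWWT). An equally spaced trend has weights (-1, 0, +1); these are my assumption.

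- Gain d in iW and iWWT, none in iT: trend changes by -d + 0 + d = 0. The iW-to-iT step changes by -d and the iT-to-iWWT step by +d.
- Gain d in iWWT only: trend changes by d.
- Gain d in iT and iWWT (a talking effect): trend changes by d.

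Because iT has weight zero, a change in iT alone does not move this slope, although it moves both steps.

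**3. Power.** The documents give no SD, correlation or effect size for the scores. I assume 24 completers per arm (Section 9.2), unit SD for each condition and visit, a common correlation ρ among a participant's six scores, a gain at post in the motor imagery arm only, and a two-sided t-test at 0.05 on pre-to-post change. For weights w and gains e:

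- variance of a participant's change = 2(1 - ρ)Σw²
- non-centrality = (Σw·e)/√variance × √(24/2), with 46 degrees of freedom

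Σw² is 2 for the trend, 0.5 for the mean of iW and iWWT, and 0.75 for the walking contrast (iW + iWWT - iT)/2. Example: 1 SD gain in both walking tasks, walking contrast, ρ = 0. The variance is 1.5, and the non-centrality is 1/1.225 × 3.464 = 2.83, which gives 79%.

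Power at ρ = 0 / ρ = 0.5:

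| Gain in (iW, iT, iWWT), SD | Trend | Mean iW/iWWT | Walking contrast |
|---|---|---|---|
| (1, 0, 1) | 5% / 5% | 92% / >99% | 79% / 98% |
| (0.5, 0, 0.5) | 5% / 5% | 40% / 67% | 28% / 50% |
| (0.8, 0, 1.2) | 10% / 16% | 92% / >99% | 79% / 98% |
| (0, 0, 1) | 40% / 67% | 40% / 67% | 28% / 50% |
| (0, 1, 1) | 40% / 67% | 40% / 67% | 5% / 5% |

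The loss does not need exact equality: in the third row the trend still has only 10% to 16%. When only iWWT gains, the trend does as well as the mean score and better than the walking contrast. The last row shows that a talking effect moves the trend and the mean score but not the walking contrast.

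**4. If the criterion is order and not slope.** A separate simulation assumed baseline scores 0, 0.5 and 1, between-person SD 1, residual SD 0.5 and a gain of 0.5 in iW and iWWT. The share of trained participants with a strictly increasing order at post fell from 54% to 43%. The trend then does move, but towards looking weaker.

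**The case against.** A reader might infer that the ordinal trend is the plan's only BOLD test, and that the trial therefore cannot show the change it names. The documents do not support either statement.

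- Section 9.2 has a second BOLD comparison in view, the SPM between-group contrast. This stands against the word only. It does not close the gap: Section 9.4 never takes it up, the contrast and the visit are not named, and it is described as a main effect of imagery condition and not as a difference in pre-to-post change.
- Section 9.4.2 already yields a score for each task condition, so an equal gain would be visible in the iW and iWWT scores to the extent that the pattern overlaps the walking network. This stands too. What is missing is a statement that those scores will be compared between arms and visits.
- Exact cancellation needs equal gains and equal spacing. The plan calls the trend monotonic, not linear, and the gait analysis in Section 9.4.1 looks for a three-way interaction with trial type, so unequal effects are contemplated. Unequal effects do not fully cancel, as the table shows.
- Aim 2 covers executive function as well as gait, and Section 5.1 has participants practise iT throughout. A trend driven by task load is a legitimate question for this trial. It differs from the outcome in Section 9.1.2.
- OrT-CVA is multivariate, and the three-score model simplifies it. The plan derives patterns at each visit for each arm and cites methods papers for the technique. Any comparison rule in those papers cannot be judged here; the plan itself states none.

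**Conclusion.** The concern holds as a mismatch between outcome and analysis. The BOLD analysis carried into Section 9.4 is insensitive to a training gain of similar size in iW and iWWT, and no arm-by-visit test of those conditions is pre-specified. The zero for equal gains under equal spacing is algebra and needs no SD. The powers (5% against 79% to 98% for the walking contrast with equal 1 SD gains; about 40% to 67% for the trend if only iWWT gains) rest on assumed SDs, correlations and gains and are illustrative. It would be too strong to say that the trial cannot detect gait-related BOLD change, since the scores needed are already an output of the plan. The practical risk is misreading a null or weakened trend. For a secondary outcome in a 48-person pilot, this should be corrected before analysis but does not threaten the trial.

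**What to change.** In Section 9.4.2, name one test of the BOLD secondary outcome: the between-arm comparison of pre-to-post change in a single summary, with all scores taken from one pattern common to both arms and visits so that they share a scale. Two summaries are suitable, and the choice should be made in advance:

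- **Mean iW/iWWT score.** Closest to the wording of the outcome and the more powerful when both conditions gain, but it also responds to a talking effect within iWWT.
- **Walking contrast (iW + iWWT - iT)/2.** Removes the talking component if walking and talking add, which is an assumption. It is weaker if only iWWT gains, or if iT gains along with the walking tasks.

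Keep the iW < iT < iWWT trend as a separate task-load (executive) analysis, and state that it will not be read as evidence for or against gait-related BOLD change. Add iW against baseline only if the scan design has a rest condition; Section 5.1 describes none. Reconcile Section 9.2 with Section 9.4.2 so that the comparison sized is the comparison analysed, and state the SD behind the 16 per group.

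The cost is SAP wording and one extra imaging comparison to count. The main option uses scores from scans already planned and needs no further participants.

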3 STUDY DESIGN

Design: We propose a single-blind study of cognitively-healthy older adults randomized to a phone-based motor imagery or visual imagery (active control) intervention for 12 weeks (36 sessions)

Outcomes: The primary outcome is post-intervention change in gait speed during actual walking and walking while talking.

Secondary and tertiary outcomes include improvements in cognitive performance during Talking and Walking While Talking, changes in blood-oxygen-level dependent signal during Walking and Walking While Talking, improvement in executive function, and other mobility-related cognitive processes (speed of processing, memory and spatial navigation), and improved gait variability and other quantitative gait parameters during walking and walking while talking (see Clinicaltrials.gov-NCT02762604 for a comprehensive list).

Study population: 48 Bronx and Westchester county residents between 65 and 85 years old will be randomized into a phone-based motor imagery or visual imagery (control) intervention for 12 weeks (36 sessions)

Study location: Pre and post-intervention visits will be held at the Albert Einstein College of Medicine.

Approximate duration of enrollment period and follow-up: Potential recruits who meet eligibility criteria on the telephone are invited to baseline assessment and then randomized to motor imagery or visual imagery intervention. Baseline study assessments are limited to 180 minutes over 1 day to avoid fatigue. Telephone assessments are 15 minutes. Post-intervention assessments will be conducted within 4 weeks of the completion of the intervention.

We plan to enroll and randomize 48 participants over 36 months (1-2 per month). If necessary, we will ask for a no cost extension to allow for additional time to process and analyze the data, write manuscripts, and possibly apply for a follow-up grant.

Randomization and Blinding: We will include a number of methods to reduce bias.

- Selection bias will be reduced by concealing treatment allocation until the participant is entered into trial.
- Primary outcome is an objective endpoint (gait speed) and not subjective mobility complaints.
- Motor imagery and visual imagery interventions will be administered individually, and at non-overlapping times.
- Participants and study staff will be instructed not to disclose group assignment or details of interventions.

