9.2 Sample Size and Randomization

The primary hypothesis examines change in gait speed (during NPW and WWT conditions). Setting an alpha level of .05, power of .80 and a medium effect size of defined as $f=.25$, the necessary sample size for detecting an interaction between time of test (pre and post), trial type (W or WWT) and imagery condition (Imagined gait or AC) is $n = 34$. Thus, our study completion goal of $n = 48$ (58 enrolled; 48 completed) is sufficient to detect our effects of interest and account for the 18% attrition rate expected during the study period (as observed in our previous studies (64)).

To detect a BOLD signal change at the individual subject level (i.e. first-level time-series modeling using SPM) at $p < 0.001$, a percent signal change of 0.34% is required using a published method and estimate of noise at a magnet strength of 3.0 Tesla (65). Based on this estimate, to detect a difference in contrast values between groups (i.e. second level analyses using SPM) at $p < 0.001$ and a power of at least .80, where the mean of one group's signal change is 50% of the other, 16 subjects per group are required. Thus, our study completion goal of $n = 48$ (24 in each condition) is sufficient to detect a main effect of imagery condition (imagined gait vs. AC) and leave room for the detection of interactions

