9.4 Data Analyses

9.4.1 Primary outcome.

To examine gait speed during W and WWT we will use repeated-measures analyses that include time of test (pre and post), and trial type (W or WWT) as within subjects factors, and imagery condition (imagined gait or AC) as the between-subjects factor. Consideration of these analyses will focus on the three-way interaction between time of test, trial type, and imagery condition.

9.4.2 Secondary and tertiary outcomes.

Similar repeated-measures analyses will be used for our secondary outcomes measures/additional EF measures: Trail Making Test, the Letter Number Sequencing Test, the Stroop Color and Word Test, and the Flanker Interference Task. These measures include the time to complete Trails B corrected for Trails A from the Trail Making Test (Trails B-A), the raw score from the letter-number sequencing task WAIS-III, the raw response time to Color-Word (incongruent) trials corrected for Color (congruent) trials from the Stroop Color and Word Test (i.e., Stroop Interference) and the flanker interference response time measure (incongruent-congruent trials) from the Flankers interference task. Although three of these four measures are difference scores, our analyses will be completed on raw scores in order to maximize power. More specifically, for these measures we will use repeated-measures analyses that included time of test (pre and post) and trial type as within subjects factors, and imagery condition (imagined gait or AC) as the between-subjects factor. Trial type for the Trail Making Test will be Trails A and Trails B. Trial Type for the Stroop Color and Word Test will be congruent trials and incongruent trials. Finally, trial type for the Flanker task will be congruous and incongruous trials. Consideration of these analyses will focus on the three-way interaction between time of test, trial type, and condition. Analyses will focus on the primary outcome variables during training and to the end of training period.

All behavioral analyses will be corrected for multiple comparisons using the Bonferroni correction.

We will use a whole-brain multivariate Ordinal Trend Covariance Analysis (OrT-CVA) to analyze the BOLD signal during imagined walking and walking while talking (66, 67). This is because we are interested in determining how the use of the entire locomotion and executive

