Age, sex and education will be covariates in all analyses. Given that is a pilot RCT on a fairly small sample of participants, it is not statistically feasible to control for more than the basic covariates listed above. Additional variables/potential covariates will be recorded and carefully examined for potential inclusion as covariates or outcome measures in upcoming full-scale RCT, including stride length (cm), double support time (s), cadence (steps/min), swing time (s), stance time, stride length variability (SD), swing time variability (SD), the Geriatric Depression Scale (54), Medical Illnesses and Medication questionnaires (26, 55), Cognitive and Physical leisure activity questionnaire (56-58), Falls (59), Smoking and alcohol consumption questionnaires, Obesity (assessed with weight, waist circumference, and BMI (kg/m²)), Vision (Snellen's chart), Disability (7 ADLs using the scale developed by Gill and colleagues (60, 61), IADL (62, 63), Blood pressure (Sitting/Standing), Gray Matter Volume/Atrophy (T1-Weighted structural images) White Matter Integrity (Diffusion Tensor Imaging; DTI) and White Matter Hyper intensities (Fluid-Attenuated Inversion Recovery; FLAIR).

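### The primary gait-speed test uses baseline only through a pre-to-post change contrast; a baseline-adjusted model is slightly more precise for each speed and possibly clearly more precise for the planned interaction

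*Combined protocol and SAP*

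**What the plan says.** Section 3 defines the outcome as a change: "The primary outcome is post-intervention change in gait speed during actual walking and walking while talking". Section 9.4.1 plans "repeated-measures analyses that include time of test (pre and post), and trial type (W or WWT) as within subjects factors", with imagery condition as the between-subjects factor, and names the effect of interest: "Consideration of these analyses will focus on the three-way interaction between time of test, trial type, and imagery condition".

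The covariate statement closes section 9.4: "Age, sex and education will be covariates in all analyses". The reason given for stopping there is that in a small pilot "it is not statistically feasible to control for more than the basic covariates listed above".

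Section 9.1.1 reports test-retest reliability above 0.9 for gait speed (given as a kappa) and r = 0.935 for WWT speed in 31 subjects. Section 9.2 gives a required total of 34 for the three-way interaction (alpha 0.05, power 0.80, f = 0.25) and a completion goal of 48.

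**The concern.** With two time points, any condition-by-time term is a comparison of change scores between arms. The three-way term is the arm difference in change of the W–WWT difference. A change score fixes the slope of post on pre at 1. Baseline adjustment estimates that slope, and in a randomised trial it is, apart from the cost of estimating it, never less precise. All participants have gait measured at baseline (section 6.1), so with 24 completers per arm the question is how much precision the fixed slope gives away.

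**Working it through.** **1. The plan's sample size.** For a two-arm, two-measure interaction, λ = f²·N·m/(1−ρ), on 1 and N−2 df. The plan states no correlation. With m = 2 and ρ = 0.5 (assumed), N = 34 gives λ = 0.0625 × 34 × 2 / 0.5 = 8.5 on 1 and 32 df, and power 80.7%; N = 32 gives 78.1%. So 34 reproduces. With m = 2, ρ = 0, 0.7 and 0.9 give 66, 22 and 10. At N = 48, λ = 12 and power is 92.4%.

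**2. Change contrast against baseline adjustment.** With equal pre and post SDs, and in units of the variance of a post-only comparison:
- change contrast: 2(1−r)
- baseline-adjusted: 1−r²
- ratio, adjusted to change: (1+r)/2

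**3. Each speed separately, at the section 9.1.1 values.**

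| r | Change | Adjusted | Ratio | CI narrower by |
|---|---|---|---|---|
| 0.90 | 0.200 | 0.190 | 0.950 | 2.5% |
| 0.935 | 0.130 | 0.126 | 0.9675 | 1.6% |

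The gain is 3–5% of variance. With 24 per arm and an effect that gives the change contrast 80% power (standardised difference 0.826 on change), dividing that effect by √ratio gives 82.0% at r = 0.90 and 81.3% at r = 0.935. On the plan's own effect scale, with 48 completers and one df charged, power goes from 92.4% to 93.5% and 93.1%.

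**4. Cost of estimating the slope.** With 48 participants in two arms, the adjusted variance is inflated by about 1 + 1/(48−4) = 45/44. The ratios become 0.950 × 45/44 = 0.972 and 0.9675 × 45/44 = 0.989. A simulation with 24 per arm and three further covariates gave power of 77.1% (change) and 78.2% (adjusted) at r = 0.90, and 77.3% and 77.5% at r = 0.935. After this cost the gain for a single speed is about one point or less.

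**5. The planned interaction.** The relevant r is the pre-post correlation of the W–WWT difference. Assume equal variances, the same retest value R for both speeds, and a W–WWT correlation c that is the same within and across visits. Then r_D = (R−c)/(1−c). The plan does not give c; 0.5–0.8 is assumed.

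| R | c | r_D | Ratio (1+r_D)/2 |
|---|---|---|---|
| 0.935 | 0.5 | 0.435/0.5 = 0.87 | 0.935 |
| 0.90 | 0.5 | 0.4/0.5 = 0.80 | 0.90 |
| 0.935 | 0.8 | 0.135/0.2 = 0.675 | 0.838 |
| 0.90 | 0.8 | 0.1/0.2 = 0.50 | 0.75 |

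The gain is 6.5–25% of variance before the slope cost (0.935 × 45/44 = 0.956 and 0.75 × 45/44 = 0.767 after it). At the favourable end, r_D = 0.50, 80% power on change becomes about 90%, or 89% after the slope cost.

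**6. Chance baseline imbalance.** The standard error of the baseline difference is √(2/24) = 0.289 SD, and the change estimate moves by (1−r) times the imbalance. The excess variance of the change contrast is 2(1−r) − (1−r²) = (1−r)², which is exactly this imbalance term. At r = 0.935, a one-SE imbalance moves the estimate by 0.065 × 0.289 = 0.019 SD, against a standard error of √(0.13 × 2/24) = 0.104 SD.

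**The case against.** The strongest reply is that the planned analysis already uses baseline, is unbiased under randomisation, and captures nearly all the available gain for each speed: 0.20 against 0.19 at r = 0.90. The short covariate list is also a deliberate choice for a small pilot. All of this stands except the last step. One baseline covariate costs one of about 43–46 error degrees of freedom, so the feasibility remark does not rule it out.

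Three stronger readings are tempting, and the documents do not support them:
- **That baseline is ignored.** The covariate sentence alone suggests this, but 9.4.1 has baseline as the pre level of time.
- **That each gait-speed comparison loses some ten points of power.** This needs r near 0.5 for a single speed, and the only retest figures in the plan are above 0.9. Reproducing N = 34 with 0.5 does not show that the plan expects that value, since it states none.
- **That chance imbalance biases the result as a second harm.** Step 6 shows that it is the same variance loss counted again.

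**Conclusion.** The point holds as a modest efficiency improvement, not as the correction of an error. For W or WWT speed alone the gain is about 3–5% of variance and at most 1–2 points of power, close to nil at r = 0.935 once the slope is paid for. For the three-way interaction that 9.4.1 actually tests, it is about 6.5–25% of variance.

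The second range depends on an assumed W–WWT correlation of 0.5–0.8 and the equal-variance structure in step 5. Both ranges use retest values as proxies for the correlation between baseline and weeks 12–16: one is a kappa, the other comes from 31 subjects, and no retest interval is stated. A lower correlation over the trial would make both gains larger.

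**What to change.** Replace the change contrast in 9.4.1. Do not simply add baseline speed to the covariate list: while pre remains a level of the outcome, that would put baseline on both sides of the model. Either of these forms works:
- **Separate regressions.** For the planned interaction, model the post-intervention W–WWT difference on arm, the baseline W–WWT difference, age, sex and education. For each speed, model post-intervention speed on arm, baseline speed in the same condition, and the same three covariates.
- **One likelihood model** for W and WWT at both visits, with baseline means constrained equal across arms. This keeps the three-way contrast in a single model.

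Two condition-specific models on their own would drop the planned interaction, so the SAP should say explicitly how it is retained. Use the same form for the cognitive and executive-function outcomes in 9.4.2, keeping their raw-score structure by trial type.

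The cost is one degree of freedom and revised SAP wording. No new data are needed.
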